2.7.1. Workstream I

Aim:

To estimate the prevalence of ASD's among adult psychiatric inpatients (including those with intellectual disabilities).

⁵ To be undertaken by participants with ID only.

Description:

This workstream will utilise a multi-phase cross-sectional design, whereby a large number of psychiatric inpatients will be tested for likelihood of ASD's with self- and informantadministered questionnaires (Phase 1- AQ, SRS-2, ASBQ-S, ASBQ-I and a basic information form), and a smaller group of patients, selected via stratified random sampling according to AQ questionnaire score (Table 2), will undergo further comprehensive diagnostic evaluation via interview-based assessment by a qualified health professional (Phase 2- DISCO-A, ADOS-2 and ASD-SCAN-3). This is a single centre study, where we will work with health professionals across at least two acute psychiatric hospital sites that are part of the same centre, the Bradgate Mental Health Unit (focussing only on the adult acute mental health wards within this site⁶) and the Agnes Unit (a unit comprised solely of specialist acute mental health wards for patients with ID), both based in Leicester, UK. Psychiatric inpatients with ID will bypass Phase 1 questionnaire testing (with all participants progressing directly to Phase 2), as well as ASD-SCAN-3 testing in Phase 2, owing to these tests having not been validated and/or developed for use in this patient group. They will be instead tested with a stigma scale, the SQID. For participants with ID, the assessing member of the research team will make a professional judgment as to which ADOS Module (1, 2, 3 or 4) is most appropriate to use, based on the participants level of verbal fluency and intellectual functioning. This is in contrast to participants without ID, whom, if participating in Phase 2, will all be assessed with ADOS Module 4. Whether the patient satisfies diagnostic criteria for ASD will be determined following the Phase 2 testing process, through the use of ICD-10-DCR and DSM-5 diagnostic criteria checklists by the assessing member of the research team.

⁶ Bradgate Mental Health Unit has other types of inpatient wards, including for eating disorders, forensic psychiatry, older person's psychiatry and a psychiatric intensive care unit. Patient's admitted to these other units will not be participating in the study.

Table 2: The probability of selection for Phase 2 according to AQ questionnaire score. This probability framework for the AQ has been validated in a previous study conducted on adult participants from a mixture of inpatient and community mental health settings (Tyrer et al., 2013). Participants with high AQ scores will have a greater probability of selection.

Questionnaire score	Probability of selection
Total AQ score	
≤19	0.1
20-24	0.2
25-29	0.3
30-39	0.6
≥40	1.0

Target Population:

People aged between 18 to 65 years (i.e. adult patients) whom have had an inpatient stay on an acute mental health ward in a psychiatric hospital. To ensure the population is representative, a cross section of all such inpatients⁷ over a defined time period will be invited to take part. This time period will likely be around 6-9 months, as the two units have an approximately combined 1000 patient admissions per year.⁸

Inclusion and Exclusion Criteria:

Inclusion criteria for the study include being between 18 to 65 years of age (on the date of psychiatric hospital admission) and being or having been a psychiatric inpatient on an adult acute mental health ward at either the Bradgate Mental Health Unit or the Agnes Unit (both based in Leicester, UK) during a predefined time period. These units serve a population of

⁷ Except in instances where their responsible clinician does not consent to their participation.

⁸ Figure obtained through liaison with the Leicestershire Partnership NHS Trust medical director [name]. Though the sample size required is 200 participants, previous similar studies suggest that 43-75% of potential participants will refuse to participate in the study (Tyrer et al., 2013). This is discussed at greater length in the next subsection, entitled 'Sampling and Sample Size.

approximately 1 million people living in both urban and rural areas within Leicester, Leicestershire and Rutland (Leicestershire Partnership NHS Trust, 2018).

Exclusion criteria include patients under the age of 18 years, over the age of 65 years and/or having no history of being a psychiatric inpatient. Patients with a clinical diagnosis of dementia will be excluded on the basis of the practical difficulties of conducting ASD testing in this patient group (van Niekerk et al., 2011); patients will not be excluded on the basis of any other clinical conditions. Also, patients lacking capacity will be excluded if they become distressed by the assessment process (at any point) or if their guardians are not in agreement with them remaining in the study. Participants also need to be able to understand written and/or verbal English.

Sampling and Sample Size:

Participants satisfying inclusion criteria will be recruited prospectively from psychiatric hospital sites within Leicestershire Partnership NHS Trust, via a member of their direct healthcare team inviting them into the study. If the participant wishes to find out more, they would subsequently complete an expression of interest form, providing permission to be contacted by a member of the research team, as well as their contact details. The exception to this approach will be in instances where a member of the research team is a member of the direct healthcare team of the patient⁹; in such instances the research team member will approach such patients directly.

Healthcare team members of both inpatient units will be invited to a talk to introduce the study, as well as having such details sent out to them via the Leicestershire Partnership NHS

⁹ Based on the current research team, this situation would apply to all inpatients of Watermead Ward at the Bradgate Mental Health Unit (where [name] is their responsible clinician) and all inpatients of the Agnes Unit (where [name] is a member of the healthcare team).

Trust communications team. Additionally, recruitment posters will be on display at both mental health units.

Phase 1 testing will involve about 200 patients (and corresponding informants), whereas Phase 2 testing will involve about 40 patients. Previous similar studies conducted locally have shown that around 75% of potential participants either refuse to take part or initially consent but do not complete the questionnaires when approached in the outpatient/community setting, though this proportion falls to approximately 43% when such individuals are approached in the inpatient unit setting (Tyrer et al., 2013). For this reason, approximately 600 patients will be invited into Phase 1, with a view to obtaining Phase 1 data for 200 participants. In the event that Phase 2 recruitment is inadequate to obtain 40 participants, the probabilities of selection (Table 1) will be revised, with a view to increasing the number of participants selected for Phase 2; this decision will be made around 6 months into the field work, which is to last a total of 24 months. Participants with ID will not be subjected to Phase 1 questionnaire testing, instead progressing directly to Phase 2 (though workstream II clinical data will be collected in all instances).

Setting:

Participants will be approached by a member of their direct healthcare team either during their inpatient hospital stay (where they will be approached at the hospital site) or contacted following their discharge from hospital. Phase 2 assessments will take place either at a Leicestershire Partnership NHS Trust hospital site, the University of Leicester or the patient's home, depending on the participant's preferences, their current clinical needs and relative availabilities of the aforementioned sites.

Data Collection and Analysis:

We will collect information from a combination of Phase 1 test completion from patients and informants and Phase 2 clinical assessment of a subgroup of these patients, conducted by the research team. Phase 1 test data will take the form of the completed questionnaires, returned either via post or collected from the patients acute mental health ward (in instances where the patients are still hospital inpatients at the time of completing these tests). Phase 2 clinical assessment data will be recorded on the relevant paper forms pertaining to the tests (DISCO-A, ADOS-2, ASD-SCAN-3 and SQID). The sequence in which these tests (as well as the APMS sections – see Workstream II) are administered will be random, to address any bias associated with interview order. The data on both the Phase 1 questionnaires and Phase 2 paper forms will be transferred to a Microsoft Excel spreadsheet on a Leicestershire Partnership NHS Trust or University of Leicester computer.

Primary Measures:

 ASD assessment information: 1) Questionnaire findings – AQ, SRS-2, ASBQ-S and ASBQ-I; 2) Clinical assessment findings – DISCO-A, ADOS-2, ASD-SCAN-3, SQID¹⁰, and ICD-10-DCR and DSM-5 ASD diagnostic criteria.

Analysis (Prevalence):

The purpose of analysis will be to estimate the overall prevalence of ASD's within the Leicestershire adult psychiatric inpatient population. This will be calculated based on the proportion of Phase 2 participants who meet the ICD-10-DCR and DSM-5 diagnostic criteria for ASD's on clinical assessment, with adjustment for selection and non-response, as well as the different study designs for the ID and non-ID patient subgroups. Microsoft Excel, as well as a dedicated statistical software package – either SPSS or R – will be used to assist data analysis.

¹⁰ Not part of the ASD assessment itself directly, but rather a measure of stigma, incorporated following consultation with patients with ID and their carers.

Blinding:

The study will be completed under double-blind conditions, whereby neither the patients nor the health professionals completing the Phase 2 clinical assessment will have knowledge of the patient's corresponding Phase 1 test findings. Parties who may be aware of the Phase 1 test findings will be asked not to share this information with the health professionals involved in the diagnostic assessment process. Where such information is inadvertently shared, the parties involved will be asked to report such incidents to the research team.

2.7.2. Workstream II

Aim:

To examine the association between ASD's and other psychiatric and physical comorbidities among the adult psychiatric inpatient population.

Description:

This workstream will collect clinical data for all patients included in Phase 2 of the SPRINT study.

Target Population, Inclusion and Exclusion Criteria and Sampling and Sample Size:

All participants included in Phase 2 of workstream I will be included in workstream II.

Setting:

Participant data will be obtained via participants completing a standardised interview, conducted when they attend for Phase 2 testing.

Data Collection and Analysis:

Data will be collected using a standardised interview, which will be completed with participants as part of the Phase 2 testing process. This interview will be comprised of several questions pertaining to their basic information and mental health, as well as the Mental Illness Diagnoses and Treatment and Physical Health Conditions sections of the 2014 APMS. For participants with ID, they may require the assistance of their accompanying informant/carer. Additionally, patients without ID will complete a basic information form as part of the Phase 1 testing process. The data from these forms will then be transferred to a Microsoft Excel spreadsheet.

Secondary Measures:

- Basic Information: 1) Date of birth 2) Sex 3) Postcode 4) Ethnic group 5)
 Employment status 6) Relationship status
- Mental Health (Psychiatric) History: 7) Date of most recent psychiatric hospital admission 8) Discharge date of most recent psychiatric hospital admission (where applicable) 9) Total number of inpatient psychiatric admissions 10) The Mental Illness Diagnoses and Treatment section of the 2014 APMS
- Physical Health (Medical) History: 11) The Physical Health Conditions section of the 2014 APMS
- General Health: 12) The EQ-5D-5L¹¹

Analysis (Comorbidity):

The primary purpose of analysis will be to describe the characteristics of the Phase 2 population (including the overall population, those found to meet ASD diagnostic criteria on testing and those found to not meet ASD diagnostic criteria on testing), as well as

¹¹ To be undertaken by non-ID patients and their informants only.

establishing the prevalence's¹² of the psychiatric and physical health comorbidities described in the respective APMS sections (Table 6) in those who do (and do not) meet diagnostic criteria for ASD on Phase 2 testing. Univariate analysis will be carried out for individual comorbidities, to identify the level of their association with meeting the ICD-10-DCR and DSM-5 diagnostic criteria for ASD, relative to those who do not meet such criteria, as well as corresponding OR, 95% CI and p-values¹³. As for workstream I, Microsoft Excel, as well as a dedicated statistical software package – either SPSS or R – will be used to assist in data analysis.

Table 6: The psychiatric and physical health conditions outlined in the corresponding sections of the 2014 APMS (McManus, Bebbington, Jenkins, & Brugha, 2016).

Mental Illness Diagnoses and Treatment Section	Physical Health Conditions Section
• A phobia	Cancer
Panic attacks	• Diabetes
Post-traumatic stress disorder	• Epilepsy/ fits
• ADHD or Attention Deficit Disorder	• Migraine or frequent headaches
(ADD)	• Dementia or Alzheimer's disease
• Bipolar disorder (or 'manic	• Cataracts/ eyesight problems
depression')	• Ear/ hearing problems
Depression	• Stroke
Post-natal depression	• Heart attack/ angina
• Dementia (including Alzheimer's)	• High blood pressure
• An eating disorder	Bronchitis/ emphysema
Nervous breakdown	Asthma
A personality disorder	• Allergies
Psychosis or schizophrenia	• Stomach ulcer or other digestive
• OCD	problems

¹² In the case of psychiatric comorbidities, we will be looking at lifetime prevalence, whereas for physical health comorbidities we will be looking at prevalence since that age of 16 years, in keeping with the methodology of the APMS 2014 survey, and potentially enabling later comparison of SPRINT study comorbidity data with 2014 APMS data.

¹³ To establish whether there are statistically significant (p=<0.05) differences between those participants meeting diagnostic criteria for ASD on Phase 2 testing, in comparison to those who do not meet said criteria.

Seasonal affective disorder	Liver problems
Alcohol or drug dependence	• Bowel/ colon problems
• Any other anxiety disorder	Bladder problems/ incontinence
• Any other mental, emotional or	Arthritis
neurological problem or condition	• Bone, back, joint or muscle
	problems
	Infectious disease
	• Skin problems
	• Other (please specify)

Blinding:

The health professionals assessing participants in Phase 2 will be blinded to the Phase 1 assessment findings (i.e. questionnaire data from workstream I). Parties who may be aware of such findings will be asked not to share this information with the health professionals completing Phase 2 interview-based assessments. As for workstream I, where such information is inadvertently shared, the parties involved will be asked to report such incidents to the research team.

2.8. Statistical Review:

The statistical aspects of the study, including sample size, have been reviewed by statisticians based at the University of Leicester ([name] and [name]). The sample size was calculated through the use of a statistical textbook and related software (Machin, Campbell, Tan, & Tan, 2011), whereby for a significance level of 0.05 and power of 85%, assuming estimates of 1% community ASD prevalence and 5% inpatient ASD prevalence (Tromans, Chester, Kiani, Alexander, & Brugha, 2018), a required sample size of 374 patients is required.

Ideally, we would be subjecting a minimum of 374 patients to Phase 2 testing. This is because only participants completing Phase 2 interview assessments will yield data pertaining to the primary outcome variable (i.e. the presence of absence of satisfying diagnostic criteria for ASD). However, this is not feasible owing to resource limitations. For this reason, around 40 patients (from the minimum of 200 subjected to Phase 1 testing) will be selected, via stratified random sampling, for Phase 2 testing. Our results will be based on the assumption that the data for these 40 patients is representative of the larger group subjected to Phase 1 testing. Owing to the aforementioned sample size, the SPRINT study should be considered a pilot/feasibility study, with a view towards potential expansion of the study population upon its completion.

2.9. Consent:

Over a designated time period, potential participants will be contacted via members of their direct healthcare team based within acute mental health wards on the two sites. The research team will then contact individuals whom have consented to be contacted by them, with a view to providing further, more comprehensive study information.

This information will explain the purpose and nature of the study, what their involvement would entail and the alternatives to taking part. The entirely voluntary nature of taking part in this study will be emphasised, as well as the option to withdraw from the study at any time. Additionally, all potential participants will have the opportunity to ask any further questions about the study to the research team.

Though informants are not disclosing information about themselves in this study, but rather reporting their view about the patients, they also will be consented for both phases of the study and will have the same rights as research participants as the patient members.

For Phase 1 participation, consent will be undertaken in person (following participants completing expression of interest forms, indicating consent to be contacted by a member of the research team). The member of the research team will discuss the study further, explaining what is expected of them, checking their level of understanding and answering any questions. They will also assess the ability of the participant to complete the Phase 1 questionnaires in a meaningful manner, via testing with a sample of seven specimen questions (similar to, but not the same as, those featured within the AQ, ASBQ-S and EQ-5D-5L questionnaires). If the participant is still interested in participating, the research team member will then provide a study information pack, as well as the Phase 1 questionnaires and a study consent form in a pre-paid envelope. Upon receipt of the signed consent form by the research team, they will countersign the form and return a copy to the patient (retaining one copy for their own records).

For Phase 2 participation, participants will be contacted either via telephone or in person to inform them of their selection and invite them and their informant for a meeting in person with a member of the research team. All participants will be seen in person by a member of the research team as part of the consenting process for Phase 2. This is for the purposes of assessing their capacity and that, where they lack capacity, ensuring that appropriate personal consultee arrangements are in place and followed. The consenting process will involve assessing whether the participant has capacity to consent in accordance with the Mental Capacity Act (2005) (Department of Health, 2005). This involves a 2-stage test of capacity, including firstly establishing whether the participant has an impairment of their mind or brain, and secondly whether such an impairment (if present) means that the participant is unable to make a specific decision (such as participating in Phase 2) when required. The Mental Capacity Act requires individuals to be able to understand the decision to be made, retain information pertinent to the decision, weigh such information up in making their decision,
and be able to communicate their decision. All research team members will have relevant training and experience in assessment of mental capacity.

For both phases of the study, the participant will be allowed as much time as they wish (and no less than 24 hours for Phase 1) to consider the information, and the opportunity to question the investigator, their GP or other independent parties to decide whether they will participate in the study. Participants will be advised that they can withdraw from the study at any time. Written informed consent will then be obtained by means of participant dated signature and dated signature of the person who presented and obtained the informed consent. The person who obtained the consent must be suitably qualified and experienced, and have been authorised to do so by the Chief and Principal Investigator, as detailed on the Delegation of Authority and Signature log for the study. The original signed form will be retained at the study site within the Trial Master File. A copy of the signed Informed Consent will be given to participants and a copy retained by the research team.

Adults lacking capacity to consent for themselves will be included where possible. This is because in order to reliably estimate the prevalence of ASD's in an adult psychiatric inpatient setting, it is important to include as representative a study population as possible. Exclusion of potential participants lacking capacity would likely exclude a subgroup of patients that are disproportionately more (or less) likely to have ASD's than those with capacity. For example, patients with ID have a greater likelihood of lacking capacity, and thus exclusion of those without capacity would impact on the reliability of the results pertaining to this patient group. Additionally, the nature of the procedures utilised in this study are all non-invasive and unlikely to cause significant harm to the participants concerned. Nevertheless, if the procedures were to cause the participant significant distress and/or the participants' guardian no longer wished for them to remain in the study, they will be withdrawn from the study. Any data collected up until the point of withdrawal will be retained and used in the study analysis. In circumstances whereby a participant lacks capacity to consent to take part in the study, a personal consultee will be identified to act on their behalf. This individual would be someone who cares for the participant or is interested in their welfare (likely either an unpaid carer, long-term partner or close relative), and is prepared to be consulted. The personal consultee will be informed about all aspects of the study which are relevant to their decision, including being provided with relevant information, given time to make a decision, and being able to ask questions to a member of the research team. Additionally, despite their lack of capacity, as much information as possible (in a form of communication that they can best understand) will be provided to the participant. Wherever possible, the study procedures will also be conducted in a setting that is familiar to the patient, such as their home, to minimize their discomfort and inconvenience. If their continued participation is causing them significant distress, they will be withdrawn from the study. Similarly, if their personal consultee is not in agreement with their continued participation, they will be withdrawn from the study. Any data collected up until the point of withdrawal will be retained and used in the study analysis. In the event that a participant should lose capacity to consent during the study, their initial consent would not legally endure, and an appropriate personal consultee would need to be

found before potentially continuing with the study.

2.10. Payments:

For Phase 1, participants and informants will each receive a £5 high street gift voucher as payment for their participation in the study. For Phase 2, both participants and informants will receive £15 high street gift vouchers as payment for their participation in the study. In situations where participants are required to travel, their travel expenses will be reimbursed. However, wherever possible, the member of the research team will travel to the residence of the participant (or the hospital in cases where they remain an inpatient at this time).

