The Stigma Questionnaire for people with Intellectual Disability (SQID) (Ali et al., 2008) is a 10-item scale for measuring stigma in patients with ID. It has face and content validity, as well as having been developed with a view to accommodating for the cognitive deficits present in this patient group (Werner, Corrigan, Ditchman, & Sokol, 2012). This scale was added to the project protocol following consultation with patients with ID and their carers, whom advised that stigma was an issue of particular importance to them and requested that it be incorporated into the study.

The major internationally recognised diagnostic criteria for ASD include those of the 10th revision of the International Statistical Classification of Diseases and Related Health Problems Diagnostic Criteria for Research [ICD-10-DCR] (World Health Organization, 1993) and the 5th edition of the Diagnostic and Statistical Manual of Mental Disorders [DSM-5] (American Psychiatric Association, 2013). Checklists for both of these sets of criteria will be completed by the assessing member of the research team for all Phase 2 participants, to establish whether the patient satisfies such criteria.

2.4. Aims:

- 1. To estimate the prevalence of ASD's amongst adults who have been admitted to psychiatric hospitals (including those with intellectual disabilities).
- 2. To examine the association between other mental and physical health conditions in adults who meet diagnostic criteria for ASD's with those who do not meet such criteria (all of whom have been admitted to a psychiatric hospital) and other psychiatric and physical comorbidities within an adult psychiatric inpatient population.

2.5. Objectives:

The objectives of the study are:

- Undertake ASD testing of a large adult psychiatric inpatient population, through the use of validated test questionnaires, including the Autism Quotient (AQ), the informant version of the Social Responsiveness Scale, 2nd edition – Adult (SRS-2) and the Adult Social Behaviour Questionnaire, (ASBQ, both the self [ASBQ-S] and informant [ASBQ-I] versions).³

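### Footnote 13's aim of establishing p=<0.05 differences for each of 39 conditions cannot be met with about 40 participants and single-figure ASD cases; Workstream II should be declared exploratory

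*Protocol*

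**What the plan says.** Protocol section 2.7.2, Analysis (Comorbidity), states: "Univariate analysis will be carried out for individual comorbidities, to identify the level of their association with meeting the ICD-10-DCR and DSM-5 diagnostic criteria". An OR, 95% CI and p-value accompany each comparison. Footnote 13 explains what the p-values are for: "To establish whether there are statistically significant (p=<0.05) differences between those participants meeting diagnostic criteria for ASD on Phase 2 testing".

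The conditions are those of Table 6, headed "The psychiatric and physical health conditions outlined in the corresponding sections of the 2014 APMS". It lists 17 mental and 22 physical entries, 39 in all. Dementia appears in both halves, in the physical column as "Dementia or Alzheimer's disease". The mental column includes "Post-natal depression", with no denominator given, in a study that enrols both sexes (section 1.3).

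Three other statements bear on this:
- Section 2.7.1, Inclusion and Exclusion Criteria: "Patients with a clinical diagnosis of dementia will be excluded".
- Section 2.7.2 makes description of the Phase 2 population the primary purpose of the comorbidity analysis.
- Section 2.8, on grounds of sample size, says that "the SPRINT study should be considered a pilot/feasibility study".

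The protocol gives no expected number of ASD cases and no power for Workstream II.

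**The concern.** A purpose of establishing significant differences at a fixed threshold is a confirmatory aim. Here it applies to 39 conditions at once, in about 40 people, of whom only a handful are likely to meet ASD criteria. A non-significant row then says little, because even large associations would usually be missed. An isolated significant row is weak evidence, because so many rows are examined. Many rows may have no affected person in the ASD group, and the usual OR and Wald interval then break down.

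Two kinds of row need separate handling. The dementia rows should be empty by eligibility. An OR for post-natal depression over all patients would partly reflect the sex mix of the two groups.

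The association with comorbidity is the study's second aim and its secondary outcome (sections 2.4 and 2.6). Section 2.22 sends the study's findings to clinical teams and commissioning groups, so the status of these p-values should be settled in advance.

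**Working it through.** **The plan's own figure.** The only sample-size figure is 374, in section 2.8, for 1% against 5% prevalence at 0.05 and 85% power. It reproduces as a two-sided, continuity-corrected comparison of two proportions, 374 per group. It concerns prevalence, so there is no Workstream II figure to reproduce.

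**Number of tests.** 17 + 22 = 39 conditions. Without the two dementia rows, 37 remain.

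**Expected ASD cases among about 40.**
- Planning prevalence (section 2.8): 40 × 0.05 = 2.0.
- Subgroup rates in appendix 4.1 (non-ID 5.3%, ID 19.6%) with the planned 25 non-ID and 15 ID participants (section 2.2): 25 × 0.053 + 15 × 0.196 = 1.3 + 2.9 = about 4.3, before enrichment.
- With Table 2 selection, which favours high AQ scores, scaled to 25 non-ID participants: about 4.7 to 7.4 at the same two rates. This assumes mean AQ 17 to 22 (SD 7) in non-cases and 25 to 35 (SD 8) in cases; the protocol gives no AQ distributions.
- Varying non-ID prevalence over 1.5% to 9.9% and ID prevalence over 4% to 19.6% as well gives about 1 to 10.

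**Power.** Fisher's exact test, two-sided 0.05, 6 cases against 34 non-cases, 30% of non-cases affected (an assumed base rate). The proportion among cases is p = odds/(1 + odds), with odds = OR × 0.3/0.7.

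| OR | Proportion in cases | Power |
|---|---|---|
| 3 | 56% | 18% |
| 5 | 68% | 35% |
| 10 | 81% | 60% |

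At a 20% base rate, 80% power needs an OR of about 20, 16 or 13 with 5, 6 or 7 cases. For 50% against 20%, power is 28% with 6 cases and 13% with 2. As an illustration, 3/6 against 7/34 gives OR 3.9, Wald 95% CI 0.64 to 23.4, Fisher p = 0.15.

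**Empty cells.** For a condition with 10% prevalence, the chance that none of 6 cases is affected is 0.9^6 = 0.53. With 2 cases it is 0.9^2 = 0.81.

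**False positives over 37 tests, taken as independent.**
- Nominal level: 37 × 0.05 = 1.85 expected; chance of at least one 1 − 0.95^37 = 0.85.
- Fisher's test with 5 to 7 cases of 40 has an actual size of about 0.007 to 0.030 per test for base rates of 5% to 50%. Chance of at least one: 1 − 0.993^37 = 0.23 to 1 − 0.970^37 = 0.68.
- At 6 against 34 and a 30% base rate, the size is 0.019, giving 37 × 0.019 = 0.70 expected and 1 − 0.981^37 = 0.51.

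**The case against.** The strongest defence is that this is a secondary, mainly descriptive analysis in a self-declared pilot, that ORs with intervals are already planned, and that multiplicity, choice of estimator and zero cells are commonly left to a SAP, which is not at hand. Much of this stands. The protocol does not commit to a Wald OR or any particular test, and its silence on multiplicity is not in itself an error. But footnote 13 is not silent: it states a significance aim and a threshold. A SAP correction could limit false positives, but it cannot supply power from a handful of cases. The descriptive purpose and the pilot label also argue against that aim.

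A reader might infer stronger points that the protocol does not support:
- **Two criteria sets, so 78 tests and a 98% false-positive chance.** The phrase naming ICD-10-DCR and DSM-5 may mean a single joint status, and section 2.6 defines a single primary outcome. The 98% also assumes independence between two checklists for the same disorder, completed on the same patients. It should not be used.
- **Post-natal depression will be tested in men.** The protocol only lists the item and omits a female-only denominator.
- **The dementia rows will mislead.** An all-zero row yields no test and no false claim. Table 6 takes its conditions from the APMS, and footnote 12 gives later APMS comparison as a reason for following its methods. That justifies collecting these rows, though not testing them.

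**Conclusion.** The concern holds as a mismatch between footnote 13's stated aim and what the design can deliver. With about 2 to 7 expected ASD cases, depending on prevalence and AQ assumptions, only very large associations would be detected with reasonable probability. Fewer cases would make this worse. Low power is at least as serious as multiplicity: 85% is the nominal false-positive figure, and about 23% to 68% is the more realistic range under an exact test with 5 to 7 cases. Both assume independent tests.

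It would go too far to call Workstream II uninterpretable. Counts, prevalences and ORs with honest intervals remain useful pilot output. What cannot be supported is a claim that a condition does or does not differ significantly. The missing female denominator is a secondary point, and the dementia rows are a tidy-up.

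**What to change.** - Replace footnote 13's significance aim with a statement that Workstream II is exploratory.
- Report counts, prevalences and exact or Firth-penalised ORs with 95% CIs. Label any p-values exploratory and make no p<0.05 claims.
- State that post-natal depression is analysed among women only.
- As a minor tidy-up, mark the two dementia rows as collected for APMS comparability but not tested, because dementia is an exclusion.

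The cost is protocol wording, with no new data. The downside is that no comorbidity can be called significant on the strength of this pilot.
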